11.1 Screening period (Day -30 to Day 0)

- Patients will be screened up to 30 days before tracer administration and confirm eligibility. At the screening visit demographic data/baseline characteristics, medical history, and medication will be recorded. All female subjects of childbearing potential will undergo a pregnancy test.
- Signed and dated informed consent must be obtained from all subjects prior to any protocol specific procedures being performed.
- Blood samples for serum biochemistry and haematology, will be drawn from venous blood if not already taken as part of subjects standard care within 30 days of tracer administration. ;.
- Vital signs and pulse oximetry, will be recorded and a physical examination including a limited neurological examination will be performed.
- If [⁶⁸Ga]-DOTA-peptide imaging PET/CT has been performed within 6 months of [¹⁸F]-FET-βAG- TOCA PET/CT, scans will be retrieved.

11.2 PET Procedure (Day 0)

The tracer is made at GMP standards, at Imanova Limited which are GMP certified

- PET/CT scans will be carried out in the Imanova Limited, at the Hammersmith hospital site, [name]
- Transportation will be arranged as required for patients
- Between 30 min to 2 min before dosing the different parameters will be assessed as reported in Table 2 (Cohort 1). Between 180 min to 5 min before dosing the different parameters will be assessed as reported in Table 3 (Cohort 2).
- For patients in cohort 1 two Intravenous cannulae will be placed in the arm in order to inject the tracer, [¹⁸F]-FET-βAG-TOCA and for metabolites (approximately 200ml of blood samples will be taken from this line). For patients in cohort 2 one Intravenous needle will be placed in the arm in order to inject the tracer, [¹⁸F]-FET-βAG-TOCA.
- Patient will be asked to lie flat on the PET-CT scanner bed
- The bed will move into the scanner which looks like a short tunnel
- Patients in cohort 1 will have ECG monitoring. Vitals will be assessed (pre-specified time points, as reported in Table 2).
- A non contrast enhanced CT will be performed to define the region of interest. [¹⁸F]-FET-βAG-TOCA will be injected intravenously. PET/CT scanning will be then subsequently performed. In cohort 1 patients will undergo 5-6 whole body sweeps (vertex to mid thighs) lasting approximately 3-4 hours with a gap in between. Patients in cohort 2 will have a PET/CT scan which will last up to 70 minutes
- Patients in cohort 1 will be admitted for overnight stay.
- Tumour biopsies at diagnosis will be retrieved for analysis of SSTR1-5 expression after Day 0 on successful completion of subject scan.

11.3 Radiation dosimetry.

Table 4. Radiation dosimetry description for [¹⁸F]-FET-βAG-TOCA PET and CT.

| Tracer | [¹⁸ F]-FET-βAG-TOCA | CT |
|-------------------------------------|--------------------------------------|--------------------------------|
| Maximum dose per scan(MBq) | 165 | |
| Conversion factor (mSv/MBq) | 0.04 | |
| Effective dose per scan (mSv) | 5.11 | 2.4 |
| No of scans | 1 | 2 (cohort 1) 1 (cohort 2) |
| Total effective dose (mSv)/ patient | 5.11 mSv cohort 1 12 mSv cohort 2 | 4.8 (cohort 1), 2.4 (cohort 2) |

Therefore total effective dose per patient is 12mSv for cohort 1 and 14mSv for cohort 2 (max dose injected 370Mbq).

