8. STUDY OUTLINE

8.1 Study design and rational of the chosen approaches

The total sample size will be 56 patients. Patients from cohort 1 (n=8-12), 4-6 female and 4-6 male (each cohort minimum 3) will be used in the final analysis. Patients with locally advanced or metastatic NETs of any site will be recruited from the Endocrinology, Surgical and Oncology Outpatients clinic, Hammersmith and Royal Free Hospitals. After obtaining informed consent, eligible patients will have blood taken at baseline for FBC, EUC, LFTs (routine clinical practice), and serum biomarkers. Patients will undergo routine staging. In addition, patients will undergo $[^{18}\text{F}]\text{-FET-}\beta\text{AG-TOCA}$ PET/CT scanning at Imanova. Patients' original diagnostic tumour biopsy (paraffin fixed) will be obtained.

8.1.1 Cohort 1. Dosimetry and safety study in patients with histological diagnosis of NETs of any site.

In this initial evaluation patients presenting for routine staging will be consented to undergo whole body dynamic scanning (multiple whole body scans up to 3.5 hours) with metabolite analysis in order to develop a suitable protocol for static scanning that will be used for patients in cohort 2. We will also calculate the internal radiation dosimetry, which may alter the administered dose in subsequent studies. Although we do not expect any toxicity, we will conduct detailed safety assessment in this group of patients. We require a minimum of 8 patients for final Dosimetry and safety analysis, which should include a minimum of either 3 male or 3 female subjects. To ensure both sexes are sufficiently represented in the final Dosimetry, for calculating effective dose, Cohort 1 will therefore include a minimum of 8, but up to 12 subjects.

8.1.2 Cohort 2. Open label study assessing tumoural uptake of $[^{18}\text{F}]\text{-FET-}\beta\text{AG-TOCA -PET}$ in patients with histological diagnosis of NETs of any site.

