13.2 Radiation dose

The total effective dose (ED) received from the PET-CT scan is estimated to be 12mSv for cohort 1 and 14 mSv for cohort 2. In a dosimetry study such as this, the estimate is necessarily uncertain but a conservative approach has been taken that will overestimate the effective dose by using a high dose conversion factor of 0.04 mSv/MBq injected activity. The total effective dose of 14 mSv (cohort2) is equivalent to about 6 times the average yearly exposure (2.3 mSv) from natural background radiation in the United Kingdom. For an adult in good health, this exposure would result in a risk of around 1 in 1600 (cohort1) and 1 in 1400 (cohort2) of contracting a fatal cancer. However, for someone in the planned study groups who have shorter life expectancy than the general population it represents a significantly lower risk. Note that as part of the standard practice for patients included in this study, a single [⁶⁸Ga] Dotatate PET/CT scan will be performed; this is one of the entry qualifications but is not an additional examination that is part of the research protocol.

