14. STATISTICAL ANALYSIS AND SAMPLE SIZE CALCULATION

14.1 Cohort 1

Using results of dynamic scanning and metabolite analysis, in particular the time course of tumour radiotracer uptake, we will design the appropriate protocol by which we will analyse the diagnostic, static scans in cohort 2. We will calculate

the internal radiation dosimetry as well as biodistribution of the tracer. Depending on these results we may alter the administered dose in cohort 2.

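### Table 4's doses do not follow from the one stated factor of 0.04 mSv/MBq, and the 165 MBq cap carries no cohort label

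*Combined protocol and SAP*

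**What the plan says.** Table 4 (section 11.3) has a tracer column with a maximum activity of 165 MBq, a conversion factor of 0.04 mSv/MBq and an effective dose per scan of 5.11 mSv. The tracer total per patient reads "5.11 mSv cohort 1 12 mSv cohort 2". Each CT is 2.4 mSv, with two CTs in cohort 1 (4.8 mSv) and one in cohort 2 (2.4 mSv). The line below the table draws the totals: "Therefore total effective dose per patient is 12mSv for cohort 1 and 14mSv for cohort 2 (max dose injected 370Mbq".

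Section 13.2 repeats 12 and 14 mSv, then says that the approach will "overestimate the effective dose by using a high dose conversion factor of 0.04 mSv/MBq injected activity". It compares 14 mSv with a yearly UK background of 2.3 mSv (about 6 times) and gives a risk of around "1 in 1600 (cohort1) and 1 in 1400 (cohort2) of contracting a fatal cancer".

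The synopsis limits activity to 165 MBq and does not say for which cohort. The cohort 2 schedule (Table 3) gives a maximum of 370 MBq, as does the line below Table 4.

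**The concern.** Activity, factor and dose stand in adjacent rows of one table column, so a reader expects the third to be the product of the first two. It is not. The totals introduced as a consequence of the table do not all follow from its cells either.

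These are the protocol's activity limit and its participant dose and risk figures. A reader who checks them cannot tell which input is wrong. Section 13.2 adds an assurance that 0.04 errs on the high side. If the cohort 2 total was not computed with 0.04, that assurance does not apply to the cohort with the higher activity.

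**Working it through.** **Inputs.** Activity: 165 MBq (synopsis and Table 4, unlabelled; taken here as cohort 1) and 370 MBq (Table 3 and the line below Table 4, cohort 2). Factor: 0.04 mSv/MBq (Table 4, section 13.2). CT: 4.8 mSv in cohort 1 and 2.4 mSv in cohort 2 (Table 4). Background: 2.3 mSv per year (section 13.2).

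**Formulas.** Tracer dose = activity × factor. Total = tracer dose + CT dose.

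**1. Plan's own totals from its own cells.**
- Cohort 1: 5.11 mSv + 4.8 mSv = 9.91 mSv; stated 12. Not reproduced.
- Cohort 2: 12 mSv + 2.4 mSv = 14.4 mSv; stated 14. Reproduced to the nearest mSv.

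**2. Totals from the stated factor.**
- Cohort 1: 165 MBq × 0.04 = 6.6 mSv tracer (printed 5.11); 6.6 mSv + 4.8 mSv = 11.4 mSv, which is 11 to the nearest mSv and 12 if rounded up.
- Cohort 2: 370 MBq × 0.04 = 14.8 mSv tracer (printed 12); 14.8 mSv + 2.4 mSv = 17.2 mSv (stated 14).

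**3. Factors that the printed cells imply.**
- Cohort 1 cell: 5.11 mSv / 165 MBq = 0.031.
- Cohort 2 cell: 12 mSv / 370 MBq = 0.0324. If 12 is a rounded value, the range is 11.5 mSv / 370 MBq = 0.0311 to 12.5 mSv / 370 MBq = 0.0338.

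**4. Could one unstated factor give both totals?** Let each total be off by up to 1 mSv in either direction.
- Cohort 1 between 11 and 13 mSv needs (11 mSv less 4.8 mSv) / 165 MBq = 0.0376 to (13 mSv less 4.8 mSv) / 165 MBq = 0.0497.
- Cohort 2 between 13 and 15 mSv needs (13 mSv less 2.4 mSv) / 370 MBq = 0.0286 to (15 mSv less 2.4 mSv) / 370 MBq = 0.0341.

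The ranges do not overlap, so no single factor yields both totals at these activities.

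**5. What follows in section 13.2 if 0.04 applies to cohort 2.**
- Excess over the stated total: (17.2 mSv less 14 mSv) / 14 mSv = 23%.
- Background multiple: 17.2 mSv / 2.3 mSv = 7.5, against 14 mSv / 2.3 mSv = 6.1.
- Risk per Sv implied by the plan: 1 divided by (1600 × 0.012 Sv) is 5.2% from cohort 1, and 1 divided by (1400 × 0.014 Sv) is 5.1% from cohort 2.
- Risk at 17.2 mSv: 0.0172 Sv × 5.2% and 0.0172 Sv × 5.1% both come to roughly 1 in 1100, against 1 in 1400. The absolute difference is under 0.02 percentage points.
- For cohort 1, 11.4 mSv gives roughly 1 in 1700 by the same method, slightly more favourable than the stated 1 in 1600.

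The plan gives its risks as approximate, so these are order-of-size figures only.

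**The case against.** The best defence is that 0.04 was never meant for cohort 2. In Table 4 it shares a column only with 165 MBq. The sentence on conservatism in section 13.2 speaks of a dosimetry study, and cohort 1 is the one that the protocol titles a dosimetry and safety study. Section 8.1.1 says "We will also calculate the internal radiation dosimetry, which may alter the administered dose in subsequent studies", and section 14.1 says "Depending on these results we may alter the administered dose in cohort 2". A higher activity in cohort 2, with a lower factor learned from cohort 1, would be legitimate. Cohort 2's own cells also agree with its total.

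Much of this stands. It makes 370 MBq the probable intention for cohort 2, so the activity point reduces to a missing label. It does not settle the factor. Those two sections concern the administered dose and state no second factor. Section 13.2 gives both totals immediately before describing 0.04 as conservative, with nothing to exclude cohort 2. Even if the defence is right, the 5.11 cells remain wrong at 0.04, and the conservatism sentence needs a limit.

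A second defence is that the cohort 1 total is only a rounding matter. That is fair for the total: 11.4 rounded up is 12, and the direction is cautious. It does not rescue the 5.11 cells, which stand in the same table and lead to 9.91.

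Third, section 13.2 concedes that "the estimate is necessarily uncertain but a conservative approach has been taken", and says that for these patients, with their shorter life expectancy, "it represents a significantly lower risk". Both points limit the practical weight. Neither explains why the figures do not follow from their inputs.

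**Conclusion.** The printed doses do not follow from the one factor stated. The 5.11 mSv cells should be 6.6 at 0.04, and as printed they contradict the cohort 1 total (9.91 against 12). The cohort 2 figures rest on a factor of about 0.032 that appears nowhere. So one of two things holds: cohort 2's dose and risk are understated (17.2 mSv and roughly 1 in 1100, against 14 mSv and 1 in 1400), or the claim that 0.04 makes the estimate conservative does not apply to cohort 2. This takes 165 MBq as cohort 1's maximum, 370 MBq as cohort 2's, and the CT doses as tabulated.

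Two stronger readings are tempting. A reader might infer that cohort 2 patients are being told too low a risk. The documents do not support that, because a lower factor may have been used on good grounds and left unstated. A reader might also infer that 370 MBq breaches the 165 MBq cap. Both statements specific to cohort 2 give 370 MBq, and a change of dose is foreseen, so the documents show an unlabelled limit and not a breach.

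Sample size and inference are unaffected.

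**What to change.** 1. State the maximum activity by cohort in the synopsis and Table 4: 165 MBq for cohort 1 and 370 MBq for cohort 2, if that is intended.
2. If 0.04 is the factor for both cohorts, change the 5.11 cells to 6.6, the cohort 2 tracer cell to 14.8 and the totals to 11.4 and 17.2 mSv. Then update the background multiple and the risks in section 13.2.
3. If a lower factor was used for either cohort, state it with its basis, recompute that cohort's cells and totals from it, and limit the conservatism statement in section 13.2 to the cohort where 0.04 was used.

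The cost is a correction to tables and text through the amendment route in section 17.4, with no change to design, procedures or sample size. There is a price in content either way. If 0.04 is confirmed for cohort 2, its stated dose and risk become less favourable. If a lower factor is confirmed, the assurance of conservatism no longer covers that cohort.

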11.4 PET parameters

Attenuation corrected images will be reconstructed. Regions of interest will be drawn around the tumour to derive semi-quantitative uptake parameters, SUV (standardized uptake value) and AUC (area under curve, total activity over scanning time). Venous blood samples will be taken for assessment of counts during the [¹⁸F]-FET- β AG-TOCA scan in cohort 1. These bloods will be used to generate the blood input function that is required to derive uptake tracer

parameters such as Ki (rate constant for net irreversible uptake) and FRT (fractional retention of tracer) which will be used to set scanning parameters for cohort 2.

12. ASSESSMENT AND FOLLOW-UP

12.1 Clinical Assessments

12.1.1 Screening

Confirm eligibility

- Complete clinical history, including concomitant medications
- Full clinical examination
- Vital signs
- ECG
- Retrieve original tumour biopsies
- Somatostatin receptor imaging within 6 months of study entry

12.1.2 Cohort 1: day of scan (Day 0)

- Confirm eligibility
- Concomitant medication recording
- Physical examination
- Vital signs
- ECG
- Bloods
- Urinalysis
- Urine pregnancy test
- [¹⁸F]-FET- β AG-TOCA PET/CT imaging
- Baseline adverse event reporting
- Cohort 1: Admit for overnight observation at the Phase I unit, Hammersmith Hospital

12.1.3 Cohort 1: Day 1 post scan

- Physical examination
- Vital signs
- ECG
- Bloods

- Urinalysis
- Adverse events reporting

12.1.4 Cohort 2: day of scan

- Confirm eligibility
- Vital signs
- [¹⁸F]-FET- β AG-TOCA PET/CT imaging
- Baseline adverse event reporting
- Urine pregnancy test

13. COMPLICATIONS AND RADIATION DOSE

13.1 Complications

All patients will be recruited strictly according to protocol following the principles of the Declaration of Helsinki. All inclusion criteria would be satisfied before approaching patients. There are no immediate complications of the PET scan except for a potential mild bruising at the site of insertion of the cannula which should resolve in 1-2 weeks.

13.2 Radiation dose

The total effective dose (ED) received from the PET-CT scan is estimated to be 12mSv for cohort 1 and 14 mSv for cohort 2. In a dosimetry study such as this, the estimate is necessarily uncertain but a conservative approach has been taken that will overestimate the effective dose by using a high dose conversion factor of 0.04 mSv/MBq injected activity. The total effective dose of 14 mSv (cohort2) is equivalent to about 6 times the average yearly exposure (2.3 mSv) from natural background radiation in the United Kingdom. For an adult in good health, this exposure would result in a risk of around 1 in 1600 (cohort1) and 1 in 1400 (cohort2) of contracting a fatal cancer. However, for someone in the planned study groups who have shorter life expectancy than the general population it represents a significantly lower risk. Note that as part of the standard practice for patients included in this study, a single [⁶⁸Ga] Dotatate PET/CT scan will be performed; this is one of the entry qualifications but is not an additional examination that is part of the research protocol.

14. STATISTICAL ANALYSIS AND SAMPLE SIZE CALCULATION

14.1 Cohort 1

Using results of dynamic scanning and metabolite analysis, in particular the time course of tumour radiotracer uptake, we will design the appropriate protocol by which we will analyse the diagnostic, static scans in cohort 2. We will calculate

the internal radiation dosimetry as well as biodistribution of the tracer. Depending on these results we may alter the administered dose in cohort 2.

14.1.1 Safety

Safety data will be collected at baseline and after the administration of the tracer. The safety of the regimen will be evaluated by the frequency and grade of adverse events. Rates will be reported with a 90% Binomial exact confidence interval. With a sample size of N=12 the maximum half-width to the confidence interval will be 0.25. Using results of dynamic scanning and metabolite analysis, in particular the time course of tumour radiotracer uptake, we will design the appropriate protocol by which we will analyse the diagnostic, static scans in sub-study 2. Rates of adverse events will be reported by grade and summarized using 95% Binomial exact confidence interval.

14.1.2 Biodistribution

The temporal variations of ¹⁸F activity concentrations in whole blood and plasma and the rate and amount of ¹⁸F activity excreted through the urinary pathway will be measured in patients and to evaluate the bio-distribution.

14.1.3 Dosimetry

We will calculate the internal radiation dosimetry as well as biodistribution of the tracer. Descriptive statistics will be used to summarize the biodistribution of [¹⁸F] following single i.v. administration of [¹⁸F]-FET-βAG-TOCA injection (mean, median, range, interquartile range, and standard deviation). Depending on these results we may alter the administered dose in sub-study 2.

14.1.4 Somatostatin receptor expression

SUV measures from [¹⁸F]-FET-βAG-TOCA PET/CT will be summarized by lesion. The correlation of SUV measures to ordinal measures of SSTR1-5 detected by IHC staining of the diagnostic biopsy (-, +, ++, +++) will be evaluated using non-parametric Kruskal-Wallis tests.

14.2 Cohort 2

Comparison will be made between FET-βAG-TOCA PET and the standard of a/cr somatostatin receptor imaging based on both a per-patient and per-lesion based analysis. Non-parametric McNemar test with Bonferroni correction for multiple comparisons will be used. The association between SSTR1-5 expression and imaging parameters obtained will be assessed. Data will be analyzed using SPSS 16.0 for Windows.

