Using results of dynamic scanning and metabolite analysis an appropriate protocol will be designed to analyse the diagnostic static scans. The internal radiation dosimetry as well as biodistribution of the tracer will be calculated. Comparison between FET- β AG-TOCA PET and standard of care somatostatin receptor imaging will be made based on

both a per-patient and per-lesion based analysis. Non-parametric McNemar test with Bonferroni correction for multiple comparison will be used. The association between SSTR1-5 expression and imaging parameters obtained will be assessed. Data will be analysed using SPSS 16.0 for Windows.

Bio-distribution and Radiation Dosimetry

Bio-distribution data in patients will consist of ¹⁸F activity content in organs and tissues of interest, ¹⁸F activity

concentrations in whole blood and plasma and of ¹⁸F activity excreted in the urine. Descriptive statistics will be generated for bio-distribution data at each time point for each organ and tissue of interest. The amount of ¹⁸F activity excreted in urine in patients will be calculated from the product of concentration of ¹⁸F activity measured in each sample and the volume of each sample for a subset of patients.

Safety

Safety parameters will be summarized using descriptive statistics

TABLE OF CONTENTS

| | |
|-------------------------------------------------------------------------------------------------------------------------------------------------------------------------------------|-------------------------------------|
| 1. SYNOPSIS | 4 |
| 2 Table of contents..... | 6 |
| 3. LIST OF ABBREVIATIONS and Definitions of Terms | 9 |
| 4. SUMMARY | 10 |
| 4.1 Cohort 1. | 10 |
| 4.2 Cohort 2. | 11 |
| 5. BACKGROUND | 12 |
| 5.1 $[^{18}\text{F}]\text{-FET-}\beta\text{AG-TOCA-PET}$ | 14 |
| 5.2 Rationale and evidence to date | 15 |
| 6. STUDY OBJECTIVES | 16 |
| 6.1 Primary objective | 16 |
| 7. STUDY ENDPOINTS | Error! Bookmark not defined. |
| 7.1.1 Primary | 17 |
| 7.1.2 Translational end-points | 17 |
| 7.2 Cohort 2..... | 17 |
| 7.2.1 Primary | 17 |
| 7.2.2 Secondary..... | 17 |
| 7.2.3 Translational end-points | 18 |
| 8. STUDY OUTLINE..... | 18 |
| 8.1 Study design and rational of the chosen approaches | 18 |
| 8.1.1 Cohort 1. Dosimetry and safety study in patients with histological diagnosis of NETs of any site. | 18 |

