7.2.2 Secondary

2. Compare diagnostic efficacy of [¹⁸F]-FET-βAG-TOCA in those patients who have had or not had or are due to have [⁶⁸Ga]-DOTA-peptide imaging. A power of $\geq 80\%$ has been chosen to conclude non-inferiority equivalence.

*Note** (All patients with a histological diagnosis of NET and lesion on CT is $\geq 1\text{cm}$ irrespective of whether they have had a [⁶⁸Ga]-DOTA-peptide scan or are waiting for one as part of their management will be included in study).*

3. Comparison of [¹⁸F]-FET-βAG-TOCA PET/CT scan and central review (nuclear medicine and radiology physician experts) of all imaging received by patient. (To account for any discrepancy that may exist between CT, [⁶⁸Ga]-DOTA-peptide imaging and [¹⁸F]-FET-βAG-TOCA PET/CT scan, then patients will be offered an MRI scan.

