14.2.1 Power and sample size determination

Power for the Wilcoxon signed-rank test is calculated by simulation using a truncated log-normal distribution parameterized according to Kabasakal et al.¹⁵ (median = 5, range = 1 to 25) to sample the total number of lesions in patients

across a range of samples. With a total of $N = 48$ patients assessed by both modalities, there will be 80% power to conclude non-inferiority equivalence if the two methods are equivalent ($\Delta = 0$).

The distributions of number of lesions detected by $[^{18}\text{F}]\text{-FET-}\beta\text{AG-TOCA}$ – PET/CT and by $[^{68}\text{Ga}]\text{-DOTA-peptide-PET/CT}$ will be summarized, and will be compared using the Wilcoxon signed-rank test with the pre-specified level of equivalence of $\Delta = 0.64$ and a one-sided alpha= 0.1.

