14.2.3 Somatostatin receptor expression

SUV measures from $[^{18}\text{F}]\text{-FET-}\beta\text{AG-TOCA}$ will be summarized by lesion. The correlation of SUV measures to ordinal measures of SSTR1-5 detected by IHC staining of the diagnostic biopsy (-, +, ++, +++) will be evaluated using non-parametric Kruskal-Wallis tests.

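### The per-lesion McNemar test in section 14.2 and the synopsis treats lesions from one patient as independent, although the plan assumes a median of 5 and up to 25 lesions per patient

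*Combined protocol and SAP*

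**What the plan says.** Section 14.2 (Cohort 2) says the two imaging methods will be compared "based on both a per-patient and per-lesion based analysis", and the next sentence names the test: "Non-parametric McNemar test with Bonferroni correction for multiple comparisons will be used". The synopsis, under statistical methods, says the same: "both a per-patient and per-lesion based analysis", followed by "Non-parametric McNemar test with Bonferroni correction for multiple comparison will be used". No other test is named for this comparison in either place. Neither mentions a patient effect, GEE, a bootstrap over patients or any other allowance for several lesions from one patient.

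Section 14.2.1 gives the planning distribution for the total number of lesions in a patient: "median = 5, range = 1 to 25". It also plans a Wilcoxon signed-rank test on lesion counts, one pair of counts per patient, with a margin of 0.64 and a one-sided alpha of 0.1. With 48 "patients assessed by both modalities, there will be 80% power to conclude non-inferiority equivalence". No alpha is stated for the McNemar tests.

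**The concern.** McNemar's test compares b, the lesions seen only on the new scan, with c, those seen only on the comparator. Under the null it treats each of the b + c discordant lesions as a separate fair coin toss. Lesions in one patient share one pair of scans, one time gap between them (the comparator may be up to 6 months old) and to some degree one tumour biology. It is plausible, though the documents do not quantify it, that they tend to be discordant together and in the same direction. The variance of b - c is then larger than the test assumes, and a few patients with many lesions can produce a small p-value by themselves.

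At stake is a planned p-value for the comparison of the new tracer with standard imaging. It could declare a difference in either direction too often.

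**Working it through.** **Inputs from the documents.** 48 patients scanned by both methods; lesions per patient truncated log-normal, median 5, range 1 to 25 (section 14.2.1).

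**Assumed, because the documents do not give them.** Proportion of lesions discordant (d), within-patient correlation (rho or ICC), log-SD of the lesion count, and a two-sided nominal level of 0.05.

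**The plan's own figure.** The 80% power belongs to the Wilcoxon test. It cannot be confirmed, since the SD of the paired count difference is not given. The SD that would yield it is 0.64 × √48 / (1.282 + 0.842) = 2.09 lesions, or 2.04 after multiplying by √0.955 for Wilcoxon efficiency. The present point does not depend on it.

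**Illustration.** With about 290 lesions and d = 0.2 there are 58 discordant lesions. Suppose one patient has 20 lesions, all seen only on the new scan, and the other 38 discordant lesions come from 38 different patients, split 19:19. Then b = 39 and c = 19.
- Unadjusted: (b - c)/√(b + c) = 20/√58 = 2.63; exact p = 0.012.
- By patient: Σ(b - c)/√Σ(b - c)² = 20/√(20² + 38) = 0.96 on 47 df; p = 0.34.

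**Design effect.** With m lesions per patient, DE = 1 + (m - 1) × ICC, where ICC is the correlation of the lesion-level paired difference. The actual error of a nominal 0.05 test is 2[1 - Φ(1.96/√DE)]. For unequal numbers of lesions, m is the size-weighted mean Σm²/Σm. This is 9.83 if the log-SD is ln(5)/2 = 0.805.

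| ICC | DE, m = 5 | error | DE, m = 9.83 | error |
|---|---|---|---|---|
| 0.1 | 1.4 | 0.10 | 1.88 | 0.15 |
| 0.3 | 2.2 | 0.19 | 3.65 | 0.31 |
| 0.5 | 3.0 | 0.26 | 5.42 | 0.40 |

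**Simulation.** True null, exact McNemar on pooled lesions, 20,000 trials per setting, log-SD 0.65 (mean 6.0 lesions per patient, about 290 in all). Three clustering models:
- A: only the direction of discordance clusters (beta-binomial).
- B: direction and frequency cluster separately.
- C: both cluster jointly (Dirichlet-multinomial).

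Type I error at nominal 0.05:

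| d | Model | rho 0 | 0.1 | 0.3 | 0.5 |
|---|---|---|---|---|---|
| 10% | A | 0.029 | 0.037 | 0.052 | 0.068 |
| | B | 0.032 | 0.042 | 0.106 | 0.213 |
| | C | 0.031 | 0.103 | 0.228 | 0.324 |
| 20% | A | 0.035 | 0.051 | 0.083 | 0.119 |
| | B | 0.036 | 0.054 | 0.140 | 0.244 |
| | C | 0.035 | 0.113 | 0.251 | 0.340 |
| 30% | A | 0.037 | 0.065 | 0.108 | 0.157 |
| | B | 0.038 | 0.069 | 0.154 | 0.265 |
| | C | 0.038 | 0.115 | 0.254 | 0.344 |

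The models differ because rho is not the same quantity in each. Under A the ICC of the paired difference is d × rho, for example 0.2 × 0.3 = 0.06. Under C it is rho itself.

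**Does Bonferroni help?** At 0.025 (two tests, assumed) and d = 20%, the errors for rho 0/0.1/0.3/0.5 are A 0.017/0.029/0.048/0.078, B 0.017/0.030/0.095/0.188 and C 0.018/0.072/0.193/0.277. The excess over the nominal level remains.

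**Clustered test.** Σ(b - c)/√Σ(b - c)² over patients, on t with 47 df, has type I error 0.025 to 0.045 at nominal 0.05 and 0.006 to 0.020 at nominal 0.025 across these settings.

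**Sensitivity to the log-SD.** At d = 20% and rho 0.3, log-SD 0.5, 0.8 and 1.0 give 0.073, 0.086 and 0.095 under A, and 0.115, 0.152 and 0.166 under B. The clustered test stays at 0.036 to 0.041.

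**The case against.** The best case against acting is about weight. Cohort 2's primary endpoint is tumoural uptake (7.2.1) and the tracer comparison is secondary (7.2.2). The margin, alpha, power and sample size all belong to the patient-level Wilcoxon test, which is sound on this point, as is the per-patient McNemar test. McNemar tests for a difference, so a false rejection does not yield a non-inferiority claim. All of this stands, and it limits the severity.

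The size is also undetermined. Lesion numbers are a planning assumption taken from a cited study, and discordance and correlation are not given. Two receptor PET tracers may agree closely. At 5% discordance the unadjusted error is 0.027 (A) and 0.034 (B) at rho 0.1, and 0.035 (A) at rho 0.3, all below 0.05; B at rho 0.3 gives about 0.08. This too stands: the omission is certain, inflation in this trial is not.

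The McNemar sentence does not repeat the words per lesion. It follows directly on the sentence that sets both units, however, and no other test is offered, so the reading is fair.

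Finally, the analysis is planned in SPSS 16.0, and the clustered test can be conservative. The first is a small obstacle, since the statistic needs only one value of b - c per patient and two sums. The second is true, and is the price of a valid test.

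**Conclusion.** The concern holds and should be fixed. As written, the per-lesion comparison treats all lesions as independent pairs, and Bonferroni does not correct that. At 10% to 30% discordance and correlation 0.1 to 0.5, the type I error at nominal 0.05 runs from 0.037 (no inflation) to 0.344. At correlation zero there is none in any model. Under A at 10% discordance there is almost none up to rho 0.3. These figures rest on the assumed discordance, correlation, clustering model, log-SD and nominal level. The missing adjustment does not depend on any of them. The primary endpoint, the Wilcoxon test, the per-patient McNemar test and the sample size are unaffected.

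**What to change.** In section 14.2 and the synopsis, replace the per-lesion McNemar test with a patient-clustered one. For each patient take b - c, and refer Σ(b - c)/√Σ(b - c)² to t with (number of patients - 1) degrees of freedom. A bootstrap that resamples patients, or GEE with patient as the cluster, would also serve. Reporting the per-lesion comparison descriptively, without a p-value, is a simpler alternative.

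The cost is wording and a few lines of programming, with no new data or visits. Power falls only when lesions are correlated. With 20% of lesions discordant and split 70:30 (assumed), unadjusted versus clustered power is:

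| rho | A | B | C |
|---|---|---|---|
| 0 | 0.85 vs 0.84 | same | same |
| 0.1 | 0.83 vs 0.79 | 0.82 vs 0.76 | 0.78 vs 0.62 |
| 0.3 | 0.80 vs 0.70 | 0.77 vs 0.55 | 0.72 vs 0.39 |

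The higher unadjusted power at rho above 0 comes with the inflated type I error.

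Optional clarifications, on which the conclusion does not rely:
- Label both McNemar analyses supportive to the non-inferiority test in 14.2.1.
- If a difference in the proportion of lesions detected is reported, define the denominator (for example lesions seen on either scan, or those confirmed by the "central review (nuclear medicine and radiology physician experts) of all imaging received by patient" in 7.2.2) and give a patient-clustered interval.
- In 14.1.4 and 14.2.3, state the unit of the test of "The correlation of SUV measures to ordinal measures of SSTR1-5 detected by IHC staining of the diagnostic biopsy": the biopsied lesion where identifiable, otherwise one SUV per patient. With 12 patients a one-value-per-patient test is conservative (type I error about 0.02).
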